Study Design

Subjects will be recruited using flyers distributed in the obstetric clinics and pathology laboratory associated with Woman's Hospital. Overweight females who are ≥ 18 years of age, had GDM in the previous 12 months (diagnosis of GDM using Carpenter-Coustan criteria according to Fifth International Workshop—Conference on Gestational Diabetes Mellitus²) and meet all inclusion/exclusion criteria will be offered participation in the study.

Major Inclusion Criteria

- Adult female ≥ 18 years to 45 years of age who experienced GDM within 52 weeks of index pregnancy
- Actual BMI ≥ 25 kg/ m²
- Written consent for participation in the study
- Patient completed lactation
- Dysglycemia (impaired fasting glucose [IFG}, impaired glucose tolerance [IGT} or IFG/IGT) and/or β -cell dysfunction postpartum requiring pharmacological intervention (except type 1 or 2 diabetes)

Major Exclusion Criteria

- Personal or family history of medullary thyroid carcinoma or in patients with Multiple Endocrine Neoplasia syndrome type 2
- History of pancreatitis
- Significant cardiovascular, cerebrovascular, renal, or hepatobiliary diseases in the past (viral hepatitis, toxic hepatic damage, jaundice of unknown etiology)
- Serum AST and/or ALT level exceeding more than twice normal laboratory values
- Uncontrolled clinically significant hypertension Fasting serum triglycerides ≥ 800 mg/dl at screening.
- Lipid-lowering medications must have been maintained at the same dose for 3 months prior to enrollment
- Cholestasis during the past pregnancy
- Presence of contradictions for GLP-1 receptor agonist or metformin administration such as allergy or hypersensitivity
- Current use of metformin, thiazolidinediones, dipeptidyl peptidase-4 inhibitors or GLP-1 receptor agonist medications.
- Use of drugs known to exacerbate glucose tolerance.
- Use of prescription or over-the-counter weight-loss drugs
- Diabetes postpartum or history of diabetes or prior use of medications to treat diabetes except gestational diabetes

- Renal impairment (e.g., serum creatinine levels ≥ 1.4 mg/dL for women and eGFR less than 60 mL/minute/1.73 m²)
- History or currently undergoing chemotherapy or radiotherapy for cancer
- Pregnancy planned during the coming two years
- Currently breastfeeding
- Exclusion criteria include any condition, which in the opinion of the investigator would place the subject at increased risk or otherwise make the subject unsuitable for participation in the study

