Oral glucose tolerance tests with glucose (G) and insulin (I) measured at 0, 30, 60, and 120 after glucose load to assess diabetes, insulin resistance and pancreatic β -cell function will be performed 32 (+4) weeks after study medications are started. Testing will be repeated at 56 (+4) weeks and 80 (+4) weeks after treatment start. The baseline blood samples from the OGTT will also be analyzed for liver enzymes, TSH, creatinine with eGFR (baseline and 56 weeks only), and lipid profile. Subjects will remain on treatment unless they are diagnosed with DM2 during an OGTT or a random blood test at which time final testing will be performed. They will be withdrawn from the study and they will be referred to a specialist for additional treatment of

diabetes. In subjects who complete 80 (+4) weeks of treatment, all study medications will be stopped and subjects will be asked to return for routine OGTT testing by their physician.

Primary Study Endpoint:

- An index of *insulin secretion in relation to insulin resistance (IS-SI)* will be calculated. Thus, β -cell compensatory capacity will be evaluated by the insulin sensitivity-secretion index (IS-SI) defined as the product of composite insulin sensitivity index and first-phase insulin release index (insulinogenic index).

Secondary Study Endpoint(s):

- Indexes of insulin sensitivity and secretion using the serum glucose and insulin concentrations obtained in the fasting state and during the 2hr OGTT with INS will be computed by several measures previously validated in women. Changes in insulin resistance –baseline {HOMA-IR} and composite insulin sensitivity index [ISI_{OGTT}], and pancreatic β -cell function (corrected insulin response [CIR_{glupeak}] and insulinogenic index [IGI])/HOMA-IR
- Anthropometric measurements [BMI, absolute body weight, waist circumference, waist: hip ratio,
- Cardiometabolic risk measures [lipids, liver enzymes; blood pressure]
- Development of diabetes, impaired glucose tolerance or impaired fasting glucose based on positive OGTT. Glucose tolerance will be defined as normal, impaired glucose tolerance (IGT) or diabetic according to the criteria of the American Diabetes Association.¹ Patients diagnosed with diabetes will be withdrawn from the study and referred to a specialized physician.

Biochemical assays and calculations

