Laboratory Measures: Hormonal and metabolic parameters will be measured at baseline (6-52 weeks postpartum), and after 32 (+4) weeks, 56 (+4) weeks and 80 (+4) weeks treatment intervention following an overnight fast. Blood samples will be obtained in the fasting state and ½, 1 and 2 h after a standardized 75-g oral glucose load. Blood samples will be centrifuged, divided into aliquots, and stored at -70°C until assayed. Plasma glucose levels will be determined with a glucose analyzer using the glucose oxidase method (Glucose Reagent Kit, Bayer Newbury, UK). Plasma insulin will be determined in all samples in duplicate by microparticle enzyme immunoassay (Abbott AxSYM System, Abbott Laboratories, Abbott Park,

IL). Levels of total cholesterol, high-density lipoprotein cholesterol (HDL-C) and triglycerides will be determined in the initial basal sample using standard enzymatic colorimetric assays on an automated clinical chemistry analyzer whereas low-density lipoprotein cholesterol (LDL-C) will be calculated according to the Friedewald equation. Serum creatinine, liver enzymes, AST, and ALT will be measured using standard automated kinetic enzymatic assay. Circulating levels of TSH and β hCG will be measured using a two-site sandwich immunoassay with direct chemiluminometric technology (Diagnostic Products, Los Angeles, CA). The intra- and interassay coefficients of variation are less than 7 and 11%, respectively, over the sample concentration range.

Insulin sensitivity and secretion:

Indexes of insulin sensitivity and secretion using the serum glucose and insulin concentrations obtained in the fasting state and during the 2hr OGTT with INS will be computed by several measures previously validated in premenopausal women.³⁵ Insulin resistance/sensitivity will be calculated using homeostasis model assessment (HOMA-IR), which is based on fasting insulin and glucose concentrations³⁶ and the Matsuda insulin sensitivity index, which takes into account mean insulin and glucose levels following oral glucose stimulation.³⁷

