The primary outcome measure is the insulin sensitivity-secretion index (IS-SI) and secondary outcome measures include changes in lipid and hepatic enzyme levels, anthropometric parameters, insulin sensitivity and pancreatic β -cell function, and glucose tolerance status. Continuous variables will be tested for normality of distribution using the Kolmogorov-Smirnov test. Natural log transformations of skewed variables will be used where necessary in subsequent analyses. For variables with highly skewed distributions, a logarithmic transformation will be done first and the geometric means reported instead. Differences in effects of drug intervention for continuous variables (in their raw or transformed state) will be compared using Subjects/Drug Treatments by trials analyses of variance (ANOVAs). This analysis provides p values for differences between groups/drug treatments (A), differences over time (B), and the interaction of group/drug treatment with time (AB). Otherwise, changes between baseline and follow-up measurements will be compared between groups by Wilcoxon's nonparametric methods. Anthropometric measurements (body weight, BMI), blood pressure, direct and indirect measurements of carbohydrate metabolism (HOMA, SI_{OGTT} , CIRgp, IGI, and ISSI), and measurements of lipid profile (total cholesterol, HDL, LDL), and liver enzymes (ALT, AST) will be considered as dependent variables. The simultaneous effect of various baseline characteristics and characteristics at certain study treatment intervals between women who did not develop diabetes and women who did during follow-up will be studied with the use of a linear multiple regression analysis. Diabetes and IGT occurrence before and after different treatment will be compared with the McNemar test (complex chi square for paired data), which formally tests for a change between the observed proportions of 2 related samples.

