All analyses will be conducted with subjects assigned to their initial treatment group, using all available data for the period of follow-up relevant to the particular analysis. Data will be analyzed on the basis of intention to treat and also on completed treatment parameters where relevant. Differences of $P < 0.05$ will be considered statistically significant. Results will be reported as mean \pm standard error of the mean (S.E.M) for quantitative variables and percentages for categorical variables unless otherwise noted. We will perform all statistical analyses using SPSS 15.0 for Windows (SPSS, Inc.; Chicago, Ill).

Study Drugs

Description

Both active drug (Liraglutide 6.0 mg/ml injection) and placebo will be supplied by Novo Nordisk A/S. as a pre-filled pen for subcutaneous injection. Each liraglutide pre-filled pen contains 18 mg/3 ml (6 mg/ml) and will deliver 30 doses of 0.6 mg; 15 doses of 1.2 mg or 10 doses of 1.8 mg; the placebo pen will deliver equal volumes of vehicle solution only. Liraglutide and placebo are visually identical.

Metformin Hydrochloride XR (extended-release) in 500 mg strength oral tablets will be purchased in bulk through the Woman's Hospital Infusion Pharmacy. Metformin hydrochloride XR is combined with a drug release controlling polymer so that drug is released slowly from the dosage form. The medication will be allocated into appropriate patient dosage regimens by the hospital pharmacy personnel. Dosage of metformin XR will be prescribed according to standard directions and not exceeding the maximum recommended daily dose in adults of 2000 mg.

Trial Supplies

Double-blind Liraglutide or placebo

Liraglutide 6.0 mg/ml or placebo solution for injection in a 3 mL pre-filled pen will be supplied by Novo Nordisk A/S. The pre-filled pen will be provided as a pen-injector. The Investigator will provide each subject with Direction for Use for the liraglutide pen-injector at each dispensing visit.

Packaging and Labelling of Trial Products

Liraglutide and placebo will be packed and labelled by Novo Nordisk A/S and provided in non subject specific boxes. Labelling will be in accordance with Annex 13, local law and trial requirements.

Storage, Handling, Accountability and Destruction of Trial Products

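### The by-trials ANOVA specifies no sphericity correction, so an uncorrected treatment-by-time test over four visits can run modestly above the stated 5%

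*Combined protocol and SAP*

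**What the plan says.** The Statistical Analysis Plan section compares continuous variables, raw or log-transformed, by "Subjects/Drug Treatments by trials analyses of variance (ANOVAs". IS-SI, the primary outcome, is in its list of dependent variables. From this analysis it takes p values for group (A), for time (B) and for "the interaction of group/drug treatment with time (AB". The same section sets the threshold: "Differences of $P < 0.05$ will be considered statistically significant". It names SPSS 15.0 but no procedure or output row.

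The Laboratory Measures paragraph gives the time points: "baseline (6-52 weeks postpartum), and after 32 (+4) weeks, 56 (+4) weeks and 80 (+4) weeks treatment intervention". The follow-up text under Randomization and Allocation agrees: after the week-32 test, "Testing will be repeated at 56 (+4) weeks and 80 (+4) weeks after treatment start". Baseline is off study drug, because the exclusion criteria rule out "Current use of metformin, thiazolidinediones, dipeptidyl peptidase-4 inhibitors or GLP-1 receptor agonist medications".

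The one distributional check planned is a Kolmogorov-Smirnov test of normality. The remedies are a log transformation or, failing the ANOVA, a Wilcoxon comparison of changes from baseline. The documents do not mention sphericity, a Greenhouse-Geisser or Huynh-Feldt adjustment, a multivariate test or a covariance structure.

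**The concern.** In a by-trials ANOVA the ordinary F tests of B and AB assume sphericity. When it fails, these tests use too many degrees of freedom and reject too often. A normality check and a log transformation are not designed to detect or repair unequal correlation between visits.

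This design makes some departure likely. One visit is untreated and three are on treatment. Baseline falls anywhere from 6 to 52 weeks postpartum. The gaps between visits are 32, 24 and 24 weeks. On-treatment values would ordinarily correlate more with each other than with baseline.

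AB is the term that asks whether the arms change differently over time, so it is a natural candidate for the treatment comparison on IS-SI and on each continuous secondary outcome. If its uncorrected p value is used, the 0.05 threshold is somewhat easier to reach than it appears. If the choice between corrected and uncorrected p values is left until the data are in, it can be made after seeing the results.

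**Working it through.** **Inputs from the documents.** Threshold 0.05. Four time points (0, 32, 56 and 80 weeks). Allocation 1:1. The Sample Size section gives 118 women, so 118/2 = 59 per arm; planned recruitment is 75 per arm.

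**Inputs assumed.** Visit correlations and SDs, because the documents give none. Data are normal with no missing visits.

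**The test.** AB has (4 − 1)(2 − 1) = 3 numerator df. Between-subject error df is 2 × 59 − 2 = 116, so the AB error df is 3 × 116 = 348. The 5% critical value of F(3, 348) is 2.63.

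**Degree of violation.** Let λ be the eigenvalues of the covariance of three orthonormal visit contrasts. Then ε = (Σλ)² / (3 Σλ²). It equals 1 under sphericity and 1/3 at worst.

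Worked example, equal SDs, baseline correlation a = 0.4 and between-visit correlation b = 0.8:
- Variance of a baseline-to-visit difference: 2(1 − 0.4) = 1.2. Variance of a between-visit difference: 2(1 − 0.8) = 0.4. They differ threefold.
- Eigenvalues: 1 − b = 0.2 (twice), and ¾[1 + (1 + 2b)/3 − 2a] = ¾ × 1.067 = 0.8.
- ε = (0.2 + 0.2 + 0.8)² / [3(0.04 + 0.04 + 0.64)] = 1.44/2.16 = 0.67.

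**Reproducing the plan's 5% first.** With equal SDs and all correlations 0.5 (ε = 1), the uncorrected AB test rejected in 5.0% of null trials. The stated level is right when sphericity holds.

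**Other patterns.** Null trials, 59 per arm, 400,000 runs each; Monte Carlo standard error about 0.04 percentage points.

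| Assumed pattern | ε | Uncorrected AB | Greenhouse-Geisser |
|---|---|---|---|
| All correlations 0.5 | 1.00 | 5.0% | 4.9% |
| Baseline 0.5, between visits 0.6 | 0.98 | 5.1% | 4.8% |
| 0.5 and 0.7, on-treatment SD 1.5-fold | 0.97 | 5.2% | 4.8% |
| 0.5 and 0.7 | 0.89 | 5.6% | 4.8% |
| Decay, 0.5 per 24 weeks | 0.88 | 5.7% | 4.9% |
| 0.6 and 0.8 | 0.82 | 6.0% | 4.8% |
| Decay, 0.7 per 24 weeks | 0.79 | 6.2% | 4.8% |
| 0.4 and 0.8, on-treatment SD 1.5-fold | 0.77 | 6.2% | 4.8% |
| 0.3 and 0.7 | 0.76 | 6.3% | 4.8% |
| Decay, 0.9 per 24 weeks | 0.69 | 6.9% | 4.9% |
| 0.4 and 0.8 | 0.67 | 7.0% | 4.9% |
| 0.3 and 0.8 | 0.62 | 7.4% | 4.9% |
| 0.2 and 0.8 | 0.58 | 7.7% | 4.9% |

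At 75 per arm each uncorrected rate was within 0.2 points of the rate at 59, so a larger sample does not remove the excess.

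**Ceiling.** At ε = 1/3 the statistic behaves as F(1, 116), and P[F(1, 116) > 2.63] = 10.8%.

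**The case against.** The strongest reply is that the plan does not choose an invalid test. It says the ANOVA provides p values and does not say which ones will be reported. The named software can supply corrected values, and the analyst may well have meant to use them. This stands: a reader might infer that the uncorrected test was selected, and the text does not support that. The gap is silence on the point.

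Four further points stand.
- The size rests entirely on assumed correlations. With 0.5 and 0.6, or 0.5 and 0.7 with larger on-treatment SDs, the excess is 0.1 to 0.2 points. Nothing in the documents shows that the harsher patterns are the likelier ones.
- AB is not named as the deciding test. A does not depend on sphericity, and neither does the Wilcoxon fallback.
- Entering all four visits in one ANOVA is an inference. With baseline and a single follow-up, sphericity would not arise.
- The simulation uses complete data, whereas the plan allows for 20-22% dropout and withdraws women who develop diabetes. The rates describe the test under stated conditions and do not forecast this trial.

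These points limit the size and scope but do not remove the issue. Under ordinary non-spherical patterns the plain test exceeds its stated level, and nothing in the plan prevents its use.

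**Conclusion.** The point holds in limited form. The plan specifies no sphericity correction. If all four visits enter one ANOVA and the plain F test is used, the false-positive rate of AB is about 5% to 7.7% under the correlations assumed here. There is no excess if sphericity holds, and the bound is about 10.8%. B rests on the same assumption.

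A reader might go further and conclude that the primary result carries a false-positive rate of 7% or more, or that 10.8% is to be expected. The documents support neither. They give no correlations and do not make AB the deciding term, and the ceiling needs the most extreme covariance possible. The importance is minor to moderate. That the plan never says whether A or AB decides the primary endpoint is the larger gap, and the same amendment can close both.

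**What to change.** In the Statistical Analysis Plan section, add that p values for B and AB will use Greenhouse-Geisser-corrected degrees of freedom. Alternatively, replace the by-trials ANOVA with a repeated-measures model with unstructured covariance. With four visits that means 4 × 5/2 = 10 variance and covariance parameters; it does not assume sphericity, and it can keep women with incomplete visits, in line with the plan's intention to use all available data.

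In the same amendment, name the term that decides the primary endpoint. If that is a single baseline-adjusted comparison of the arms at a named visit, the sphericity question does not arise for the primary test, though the correction is still needed wherever B or AB is reported.

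The cost is one or two sentences. If sphericity holds, the correction loses very little power: the simulated error rate there was 4.9% against 5.0% uncorrected.

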Gestational diabetes is a common medical problem that results from an increased severity of insulin resistance as well as an impairment of the compensatory increase in insulin secretion. A diagnosis of GDM has significant implications for the future health of the mother. Approximately 40% to 60% of women with a diagnosis GDM will exhibit further deterioration of carbohydrate metabolism. GDM is often the culmination of years of unrecognized and unmodified diabetes risk factors that lead to overt and occult clinical manifestations during pregnancy. Pregnancy, in essence, serves as a metabolic stress test and uncovers underlying insulin resistance and β -cell dysfunction. Postpartum management of women with GDM is critical because of their markedly increased risk of DM2 in the future. Women with prior GDM have substantial rates of impaired fasting glucose (IFG), impaired glucose tolerance (IGT), and DM2 after pregnancy. Women with a history of GDM are also at increased risk of other cardiovascular risk factors, such as obesity, hypertension, dyslipidemia, and the metabolic syndrome as well as subclinical atherosclerosis. Taken together, these findings suggest that GDM identifies a population of young women at increased risk for cardiovascular disease (CVD). Presently, in the literature, there are described new, more efficient methods of diabetes prevention in groups with a high risk of this disorder, which involve both, lifestyle modification and pharmacological therapies. In the 2.8 years of Diabetes Prevention Program (DPP) randomized clinical trial, diabetes incidence in a nonpregnant population with impaired glucose tolerance was reduced by 58% with intensive lifestyle intervention and 31% with metformin compared with placebo.¹⁷ . Treatment of insulin resistance with the thiazolidinedione drug, troglitazone, improved insulin sensitivity and reduced the incidence of type 2 diabetes for nearly 5 years in Hispanic women with prior gestational diabetes¹⁷. During a median follow-up of 30 months on blinded medication, average annual diabetes incidence rates in the 236 women who returned for at least one follow-up visit were 12.1 and 5.4% in women assigned to placebo and troglitazone, respectively. Clinical studies using rosiglitazone or pioglitazone for a period of 3 years have demonstrated a beneficial effect of both agents in improving insulin sensitivity and recovery or improvement of β -cell function, which are sustained in some individuals over

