The reason for a subject discontinuing from the study will be recorded in the patient chart. A discontinuation occurs when an enrolled subject ceases participation in the study, regardless of the circumstances, prior to completion of the protocol. The investigator must determine the primary reason for discontinuation. Withdrawal due to adverse event will be distinguished from withdrawal due to insufficient response according to the definition of adverse event noted earlier. The final evaluation required by the protocol will be performed at the time of study discontinuation. The investigator will record the reason for study discontinuation, provide or arrange for appropriate follow-up (if required) for such subjects, and document the course of the subject's condition. They will also to be reported to Woman's Hospital Foundation Institutional Review Board at [contact] and Woman's Health Research Department at [contact].

Sample Size Computation and Power Analysis

A priori sample size analysis was performed using the online calculator provided by the Massachusetts General Hospital Mallinckrodt General Clinical Research Center (http://hedwig.mgh.harvard.edu/sample_size/size.html). Because the possible advantages of combination treatment over metformin alone rely on the presumed positive effects of liraglutide on pancreatic β -cell function parameters, we used the difference in a surrogate marker of insulin secretion relative to insulin resistance as the primary outcome for sample size analysis. An experimental design including a total of 118 patients would have power above 0.80 to detect differences in the IS-SI index between treatments such as those previously reported using a similar experimental design.⁴⁶

We plan on recruiting 150 overweight women with a recent history of GDM to be studied. The estimated enrollment: of 75/group for an average follow up of 60 weeks of treatment (range 32-84 weeks) will be our intent-to-treat population. This sample size is projected to provide power ≥ 0.8 to detect a $\geq 20\%$ difference in insulin action indices between treatment groups at a median follow-up of 24 months. The calculation was adapted to allow for significant dropout rate (20-22%) for completion of the full trial of 80 (+4) weeks of treatment. Subjects who drop out of the trial will not be replaced

Statistical Analysis Plan:

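### Fasting and 2-hour glucose are measured at every OGTT visit but are not named as continuous outcomes, and the only planned test of glycaemic status makes no comparison between arms

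*Combined protocol and SAP*

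**What the plan says.** Study Design and the laboratory section (Biochemical assays and calculations) schedule a 75-g OGTT with glucose and insulin at 0, 30, 60 and 120 minutes, at baseline and at 32, 56 and 80 weeks. No OGTT is described at the ten-weekly drug-supply visits.

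The secondary endpoints are insulin sensitivity and secretion indices, anthropometry, cardiometabolic measures, and "Development of diabetes, impaired glucose tolerance or impaired fasting glucose based on positive OGTT". The Statistical Analysis Plan lists as dependent variables "direct and indirect measurements of carbohydrate metabolism (HOMA, SI_{OGTT} , CIRgp, IGI, and ISSI"), with weight, BMI, blood pressure, lipids and liver enzymes. These are to be compared by a treatment-by-time ANOVA, or otherwise by Wilcoxon methods on changes. For status it says: "Diabetes and IGT occurrence before and after different treatment will be compared with the McNemar test". IFG is part of the endpoint but is not in that sentence.

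Women diagnosed with type 2 diabetes have final testing and are then withdrawn.

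**The concern.** The Rationale rests partly on the combination preventing or delaying a decline in glucose tolerance. The direct measures of that are fasting and 2-hour glucose, and the plan does not say they will be compared between arms.

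The indices do not fill the gap. Each combines glucose with insulin, and the background describes GLP-1 as strongly insulin-releasing, so a change in an index does not show whether glucose fell. The 2-hour value, which is needed to classify IGT, enters only through the OGTT mean in the composite sensitivity index (and so in IS-SI), or in CIR if glucose peaks at 120 minutes.

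The status test does not fill it either. McNemar asks whether the proportion changed within the same women. Running it in each arm and comparing the two p-values is not a test of the treatment difference. Even a proper two-arm test of yes/no status would be weak at this sample size, so a null result on diabetes or IGT would say little, although the same samples could be more informative.

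**Working it through.** **The plan's own figures.** The sample size section states: "An experimental design including a total of 118 patients would have power above 0.80 to detect differences in the IS-SI index between treatments". It gives no difference or SD, so 118 cannot be recomputed. Solving backwards for 59 per arm, two-sided 0.05 and power 0.80 gives a standardised IS-SI difference of 0.516. The enrolment figure does reproduce: 118/(1 − 0.21) = 149.4, or 150 women (75 per arm). No power is stated for any glycaemic outcome.

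**Inputs for the illustration.**
- Group sizes: 75 enrolled and 59 evaluable per arm. Significance is P < 0.05; sidedness is not stated, so two-sided is assumed.
- Annual diabetes incidence from Study Background and Rationale: 12.1 v 5.4% (placebo v troglitazone) and 13.1 v 4.6% (placebo v pioglitazone).
- Optional factor of 0.69 on both rates for background metformin, from the 31% reduction cited there.
- Assumed: normal glucose, equal SDs, and treatment acting as a pure shift.

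**Formulas.**
1. Cumulative incidence over 80 weeks: p = 1 − exp(−rate × 80/52.18).
2. Power for two proportions: Φ{[|p1 − p2| − 1.96√(2p̄(1 − p̄)/n)] / √[(p1(1 − p1) + p2(1 − p2))/n]}.
3. Equivalent shift: d = z(p1) − z(p2). Power for means is that of a two-sample t-test with noncentrality d√(n/2).

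**Worked case (12.1 v 5.4%, 75 per arm).** p1 = 1 − exp(−0.1855) = 0.169 and p2 = 1 − exp(−0.0828) = 0.079. Formula 2 gives (0.0898 − 0.1056)/0.0534 = −0.296, so power is 0.38. d = −0.957 + 1.409 = 0.452, noncentrality is 2.77, and t-test power is 0.79.

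**Diabetes cut.**

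| Annual rates | 80-week risk | d | n/arm | Yes/no | Continuous | Loss (points) |
|---|---|---|---|---|---|---|
| 12.1 v 5.4% | 16.9 v 7.9% | 0.452 | 75 | 0.384 | 0.785 | 40 |
| | | | 59 | 0.314 | 0.682 | 37 |
| same × 0.69 | 12.0 v 5.6% | 0.419 | 75 | 0.286 | 0.723 | 44 |
| | | | 59 | 0.234 | 0.617 | 38 |
| 13.1 v 4.6% | 18.2 v 6.8% | 0.582 | 75 | 0.560 | 0.943 | 38 |
| | | | 59 | 0.464 | 0.880 | 42 |
| same × 0.69 | 12.9 v 4.7% | 0.540 | 75 | 0.422 | 0.908 | 49 |
| | | | 59 | 0.346 | 0.829 | 48 |

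**IGT cut** (assumed: 0.4 SD shift, 20 to 50% of controls above the cut). The treated share is 10.7 to 34.5%. At 75 per arm, power is 0.349 to 0.487 against 0.682, a loss of 33 to 20 points. At 59 per arm it is 0.286 to 0.400 against 0.577, a loss of 29 to 18 points.

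**Smaller effect.** With a 0.2 SD shift at 59 per arm, continuous power is only 0.19 and the loss is about 8 to 5 points over the same control shares.

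**Missing glucose after diagnosis.** In a simulation of the worked case, continuous power falls from 0.79 to about 0.69 if half the women above the diabetes cut have no value, and to about 0.56 if none has. The gain over 0.38 then shrinks from 40 points to about 31 and 18.

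**The case against.** - **Glucose is not discarded.** Fasting glucose enters HOMA-IR uncut, fasting and mean OGTT glucose enter the composite index, and glucose enters IGI, CIR and the primary IS-SI. A reader might infer that glucose is analysed only after being cut; the index formulas show otherwise. The SAP's reference to direct measurements also leaves some room for glucose. What stands is narrower: fasting and 2-hour glucose are not named as outcomes in their own right, although other raw laboratory values are.
- **The power figures are conditional.** A reader might infer that the trial gives up 37 to 49 points on its glycaemic outcome. The documents do not support that. The rates are from placebo-controlled studies of other drugs in Hispanic women, no glucose SD or metformin-arm rate is given, and diabetes is a cut of more than one value. Women with diabetes are excluded at entry, which strains the normality assumption. The IGT loss is lower. The yes/no power is also that of a two-arm test, not of the planned McNemar test.
- **Withdrawal at diagnosis removes the highest later glucose values.** This stands and shapes the remedy. Status counts these women, so reducing the categories to a descriptive summary could lose information.
- **The outcome is secondary in a self-described pilot.** This is true. The primary endpoint is already continuous and is unaffected.

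**Conclusion.** The point holds as a gap in the secondary analyses. Followed as written, the plan names no between-arm test of glycaemia itself: the continuous carbohydrate variables all contain insulin, and status is tested only before against after. That conclusion needs no assumptions about effect size.

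The power cost is an illustration: about 37 to 49 points for a diabetes cut and about 18 to 33 for an IGT cut at 59 to 75 per arm, under normality, equal variances, a pure shift and, for diabetes, borrowed rates. It shrinks to single figures for an effect as small as 0.2 SD, and it shrinks if diagnosed women's glucose is missing. The direction is clear; the size for this trial cannot be fixed from the documents.

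**What to change.** Add fasting and 2-hour plasma glucose, as continuous values, to the secondary endpoints and to the SAP's dependent variables. Compare them between arms over the OGTT visits with baseline taken into account. Use an analysis that keeps women withdrawn at diagnosis by including their final OGTT, for example a mixed model on all available data.

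Keep diabetes/IGT/IFG status as a secondary outcome, with IFG named in the analysis, and replace the before/after McNemar test with a between-arm comparison.

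No new sample or visit is needed. The cost is SAP wording and two more secondary tests in the multiplicity count. Glucose after withdrawal at diagnosis remains missing, so the SAP should state how this is handled and report the numbers by arm.
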